7.5.5.3 EXPECTEDNESS

The Data and Coordinating Center in consultation with the IRB/IEC, will be responsible for determining whether an adverse event (AE) is expected or unexpected based on information provided by the clinical site or through central review activities. An AE will be considered unexpected if the nature, severity, or frequency of the event is not consistent with the risk information previously described for the study intervention.

7.5.6 REPORTING EVENTS TO PARTICIPANTS

The consent form explicitly states that if an incidental finding is detected on a study scan or laboratory that may have clinical significance, the information will be provided to the research site and then the participant will be contacted by the research site and a plan will be made for medical follow-up.

MRI Clinical Read – Each research site is responsible for obtaining a clinical interpretation following local clinical practice for each MRI scan to make a determination whether additional follow-up and contact with the subject and their primary physician is indicated.

PET Clinical Read – Amyloid PET scans will be read by the PET Core; results will be reported to Site investigators, which in turn can be provided to the participant if the participant requests the result and to support clinical decision-making with regard to approved therapeutics such as aducanumab.

8 STATISTICAL CONSIDERATIONS

8.1 POPULATIONS FOR ANALYSES

The Biostatistics Core will carry out interim and final analyses of ADNI4 data, separately and in combination with previous phases, for the primary aims and hypotheses. Strategies for analysis goals are summarized briefly below.

We will use two main analytic datasets. First, the ADNI4 cohort (those recruited for ADNI4 combined with rollover participants from ADNI3) will provide information on cognitive and biomarker characteristics and change in all current measures. The newly recruited participants are critical to include a more diverse cohort. Second, we will also analyze merged data from all phases of ADNI, to facilitate analysis of progression and long-term trajectories. This will require harmonization of data collected from different protocols, assays, and tracers. All ADNI4 participants will be included in analyses except for those focused on hypotheses about specific subgroups, e.g. predictors of progression for participants who are MCI at baseline. Secondary analyses will assess the potential impact of missing data, outliers, and other questions regarding sensitivity and robustness of findings.

All analyses will follow best practices for reproducible research. Final validated code for data preparation and analysis will be shared on the LONI website and via GitHub.

8.2 STATISTICAL ANALYSIS GOALS

Goal 1: To support the design of the ADNI4 cohorts, particularly the remote blood and in-clinic cohorts. Participant referrals will be informed by results from the remote digital cohort components (questionnaire, cognitive testing) and the plasma-based AD biomarkers to ensure sample diversity for those selected for in-clinic participation, to allow testing of hypotheses and to increase generalizability to a larger population.

Goal 2: Characterize baseline distribution of biomarkers and associations. Baseline characteristics will be summarized graphically and numerically, separately for baseline diagnostic categories (CN, MCI, DEM). Associations among biomarkers and with cognitive, clinical, and functional levels at baseline will be summarized numerically and graphically. Performance of baseline biomarkers as predictors of cognitive and functional change, disease progression, and post-mortem findings will be assessed by regression models (linear, logistic, survival, etc.).

Goal 3: Assess the potential of biomarkers for use in screening, inclusion/exclusion, stratification, and covariate adjustment for clinical trials. We will report and compare predictive abilities and impact on sample size, power, and duration of study in hypothetical clinical trials. To assess the explanatory power of a candidate biomarker, we will build models incorporating additional variables (demographics, genotype, baseline clinical or cognitive status, additional biomarkers). Sex as a biological variable will be considered both as a predictor and a potential effect modifier.

Goal 4: Characterize longitudinal trajectories of biomarkers and their associations. Longitudinal change in biomarkers will be characterized using linear mixed models for continuous measures, possibly transformed to deal with floor or ceiling effects, nonlinearity, practice effects, nonnormality, or heteroscedasticity. Extensions of these models allow for the simultaneous modeling of change in multiple outcomes for estimating correlation between change in multiple biomarkers or change in a biomarker with cognitive and functional change.

Goal 5: Assess the potential associations of comorbidities and sociocultural factors with biomarker, cognitive, and functional levels and longitudinal change. We hypothesize that ethnocultural differences will be associated with differences in baseline levels and

longitudinal trajectories of biomarker, cognitive, and functional measures. This will be tested by building models as in Goals 1-4 and incorporating ethnocultural variables as primary predictors, while adjusting for age and sex. Initially the analysis will consider race/ethnicity separately from sociocultural variables, then models including both will be considered to examine intersectionality. Race/ethnicity will be included as categorical variables, while sociocultural variables (e.g., years of education, acculturation, SES) will as much as possible be included as quantitative or ordinal variables to maximize power.

Goal 6: Formally compare performance across biomarkers for all previous goals. Biomarker performance will be operationalized as a correlation (for predictor) or required sample size for a clinical trial (screening tool/outcome). Our comparison strategy first identifies dimension-free participant-level contributions to the correlation or to the formula for sample size. We compare biomarkers with Friedman's rank test to account for patient-level blocking, followed by pairwise comparisons adjusted for multiple comparisons.

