4.1.1.2 NEW IN-CLINIC PARTICIPANTS

ADNI4 is aiming to include up to 750 new participants for the in-clinic cohort with at least 50-60% URPs, and target diagnostic categories of at least 40% CN, 40% MCI, 20% DEM, and overall, an 80% amyloid positive rate.

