5.4.1.2 INCLUSION OF MINORITIES

ADNI4 will strive to enroll at least 50-60% of newly enrolled participants from Under Represented Populations (URPs) including Black or African American, Hispanic or Latino/a/x, Asian, Native Hawaiian/Other Pacific Islander, American Indian/Alaska Native adults, and persons with less than 12 years of education. We are working to include 50-60% of newly enrolled participants from URPs. Historically, ADNI has failed to enroll representative populations, just as industry and academic trials have failed in this regard; only about 10% of participants have been from URPs. In ADNI3, broadly-based outreach efforts by the Diversity Taskforce increased diversity in the cohorts; 21% of new enrollees were from URPs.

ADNI4 will deploy a scalable, intensive, and culturally-informed community-engaged research (CER) approach for recruiting ~30,000+ individuals, 50-60% of whom are URPs, to participate in the remote digital cohort, with the ultimate goal of 50-60% of new in-clinic participants coming from underrepresented backgrounds, see ADNI4: Remote protocol. ADNI4 study teams will work together to facilitate the full and immersive participation of URPs in all study components. Our multi-faceted plan includes:

- (1) Culturally-informed comprehensive CER-based Digital Engagement Campaign that will include multiple language and diverse images;
- (2) ADNI4 Engagement Team that will include:
- 2a) Community Research Liaisons (CRLs) to promote URP recruitment through community-based engagement with local clinicians and community-based organizations (CBOs). They will do screenings and triage eligible participants at the participating Diversity Recruitment Hub Sites;

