7.3.1.2 DATA ACQUISITION FOR PET SCANS

All ADNI participants will complete one amyloid PET scan and one tau PET scan every two years. Scans must be completed within 2 weeks before or 2 weeks after the in-clinic assessments at Initial/Baseline visit and at two-year intervals.

Individuals who are retained in ADNI4 from ADNI3 will continue to have amyloid PET scans with the ligand that was used in ADNI3 (either FBB or FBP) and will continue to have tau PET scans with the ligand that was used in ADNI3 (FTP). Participants that are newly recruited to ADNI4 will be assigned to tracers based on the clinical site proximity to PET tracer manufacturing sites. In ADNI4 because there are 3 possible amyloid tracers and 3 possible tau tracers, there are 9 possible combinations of tracers that new individuals will receive. Each participant will be assigned to one amyloid tracer and one tau tracer that is expected to remain stable for the duration of the study. In the United States, florbetapir, florbetaben and flortaucipir are all FDA approved tracers for PET imaging. NAV4694, MK6240, and PI2620 are not currently FDA approved and will be used under IND held by ATRI investigators. In Canada, only florbetaben is approved by Health Canada (HC) for PET imaging. Use of remaining tracers (florbetapir, flortaucipir, NAV4694, MK6240, and PI2620) will be submitted to HC by ATRI investigators for approval for use in the ADNI4 study.

Scan protocols differ for each tracer. The injected doses for each tracer are listed in the table to the right. After insertion of an intravenous line, tracer is injected outside the scanner. Following injection, participants remain in a comfortable state, usually in a chair but not in the scanner, for a period of time. Imaging times after injection are listed in the table for each tracer. Prior to each scan an x-ray CT (for PET/CT systems), or positron transmission scan (for PET-only systems) is obtained for attenuation correction of the image; an MRI scan (for PET/MRI systems) may be obtained before, after or during the PET scan. Technical details for scan acquisition will be provided in a technical manual and radiation dose exposure is provided in the technical manual. The total time commitment for a PET scan may range from about 1.5 hours to 2.5 hours.

Tracer	Injected Dose	Imaging Time (post-injection)
Florbetapir	10 mCi	50-70 min
Florbetaben	8.1 mCi	90-110 min
NAV4694	8.1 mCi	50-70 min
Flortaucipir	10 mCi	75-105 min
MK6240	5 mCi	90-110 min

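### Goal 5 compares ethnocultural groups in the pooled cohort with age and sex as the named adjusters and no term for entry route, although the recruitment targets tie underrepresented status strongly to being newly enrolled

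*Protocol*

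**What the plan says.** Section 8.2, Goal 5, hypothesises that ethnocultural differences go with differences in baseline level and trajectory of biomarker, cognitive and functional measures. It tests this with models of the kind used in Goals 1 to 4, "incorporating ethnocultural variables as primary predictors, while adjusting for age and sex". Race/ethnicity is first examined apart from the sociocultural variables (education, acculturation, socio-economic status), then together with them.

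Section 8.1 makes the first analysis set the new and rollover participants combined, and adds: "All ADNI4 participants will be included in analyses except for those focused on hypotheses about specific subgroups".

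The two routes into that set are built differently:

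- **New participants** (Sections 4.1.1.2 and 5.4.1.2): up to 750, with 50-60% from URPs and, as a target, "overall, an 80% amyloid positive rate". Sections 5.1.1.1 and 8.2 (Goal 1) provide for blood biomarker data to inform who is referred to the clinic. For PET they "will be assigned to tracers based on the clinical site proximity to PET tracer manufacturing sites", from three amyloid and three tau tracers (Section 7.3.1.2).
- **Rollovers** (Sections 4.1.1.1, 5.1.1.2 and 7.3.1.2): up to 750, with retention targets of 75% CN, 50% MCI and 15% DEM and no amyloid target. They have at least one year in an earlier ADNI phase, and they stay on FBB or FBP for amyloid and FTP for tau. On the programme they come from, Section 5.4.1.2 says that historically "only about 10% of participants have been from URPs", and gives 21% among new ADNI3 enrollees.

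**The concern.** A person from a URP in this cohort is far more likely to be new than a person who is not. New participants also differ from rollovers by design in ways that bear on the outcomes: amyloid enrichment, less prior exposure to the test battery, diagnostic mix and, for PET, tracer. A pooled contrast without an entry-route term attributes part of these differences to race or ethnicity. Age and sex are not the variables that carry them.

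Goal 5 is the analysis that serves Aim 3, on health disparities. A difference created by recruitment and reported as an ethnocultural one would be the wrong answer to one of the study's main aims.

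**Working it through.** **Inputs from the protocol.** New participants 750 and rollovers 750, total 1,500, which agrees with Section 4.1.1. URP share among new participants: 50-60%. Amyloid-positive target among new participants: 80%. The protocol states no alpha, power or effect size for Goal 5, so there is no such figure to reproduce.

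**Proxies and assumptions.** The URP share among rollovers is not stated; 10% and 21% from Section 5.4.1.2 serve as bounds. The amyloid-positive rate among rollovers is not stated; it is varied from 40% to 80%. A two-sided 0.05 level is assumed for rejection rates.

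**Step 1: how far URP status stands in for entry route.** Share new among URPs = 750·u_new / (750·u_new + 750·u_roll); the share among non-URPs uses 1 − u.

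- Weakest link (50% and 21%): 375/532.5 = 0.704 against 375/967.5 = 0.388. Difference 0.317, odds ratio 3.8, phi 0.30.
- Strongest link (60% and 10%): 450/525 = 0.857 against 300/975 = 0.308. Difference 0.549, odds ratio 13.5, phi 0.52.

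**Step 2: gap in amyloid positivity with no true difference within either route.** Gap = (difference from step 1) × (0.80 − rollover rate). At 60%, for example: 0.317 × 0.20 = 0.063 and 0.549 × 0.20 = 0.110.

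| Assumed rollover amyloid-positive rate | Gap, URP minus non-URP | Chance of a false significant difference |
|---|---|---|
| 40% | +13 to +22 points | at least 99.8% |
| 60% | +6 to +11 points | 73 to 99.5% |
| 70% | +3 to +6 points | 27 to 65% |
| 80% | 0 | 5% |

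**Step 3: does an entry-route term remove it?** Five scenarios were simulated, 1,000 runs each, with a linear probability model and robust standard errors. Rollover rates were 40%, 60% and 70%, and no true URP effect was present within either route.

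- Age and sex only: mean URP coefficient +0.033 to +0.218, false rejection 31 to 100%.
- Age, sex and entry route: mean coefficient about 0 (−0.001 to +0.001), false rejection 4.7 to 5.4%.

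Age and sex were generated independently of entry route; if rollovers differ in age, the age term would absorb some of the bias. Selection within the new cohort was taken as unrelated to race.

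**Step 4: cost.** Variance factor = 1/(1 − phi²): 1.10 at phi 0.30 and 1.38 at phi 0.52. The square roots, 1.05 and 1.17, give intervals about 5 to 17% wider.

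**Step 5: tracer, PET outcomes only.** NAV4694, MK6240 and PI2620 are expected only in new participants. If one third of new participants received NAV4694 (assumption), it would be used in 23.5 to 28.6% of URPs (0.704/3 to 0.857/3) and in 10.3 to 12.9% of non-URPs (0.308/3 to 0.388/3).

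**The case against.** The strongest reply is that Section 8 calls itself a brief summary, that a full covariate list belongs in the statistical analysis plan, and that naming age and sex excludes nothing. Goals 1 to 4 bring in description by diagnosis, genotype, baseline status, other biomarkers and attention to practice effects; the second-stage Goal 5 models add education, acculturation and socio-economic status; and Section 8.1 promises secondary analyses of robustness. So a reader who infers that the protocol permits nothing but age and sex goes too far. What remains is that Goal 5 does name an adjustment set for its primary contrast, on a named pooled population, and that none of the additional variables mentioned is entry route, site or tracer. A plan that follows this text inherits the bias.

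Other stronger readings also fail:

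- **That URP status and entry route cannot be separated.** Both groups occur in both routes, which is why the term is estimable.
- **That tracer harmonisation is confined to the merged all-phase data.** Section 8.1 raises it there, but Sections 9.1.1.5 and 9.1.1.9 give the PET and Biostatistics Cores standardisation and harmonisation tasks without that limit. Goal 5 simply does not say how it applies to the ADNI4-only set.
- **That tracer contaminates every outcome.** It affects PET measures only, and new participants may also receive FBP, FBB or FTP.
- **That every new participant was selected on plasma.** Sections 7.1.1 and 7.1.5 allow direct recruitment at sites.
- **That the study is certain to report spurious differences.** The size depends on a rollover amyloid rate that the protocol does not give, and the 80% is a target.

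Two limits of the calculation also stand. URP includes people with less than 12 years of education, whereas Goal 5 enters race/ethnicity and education separately, so URP shares only approximate the predictor. And amyloid is itself an outcome, so the enrichment is a selection effect; an entry-route term does not correct biomarker-based selection that differs by race among new participants.

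**Conclusion.** Wrong as written. The link between URP status and entry route follows from the protocol's targets and its recruitment history: odds ratio 3.8 to 13.5, strong but partial. The resulting bias in a pooled contrast on amyloid positivity is conditional on the assumed rollover rate and vanishes only if rollovers are also near 80% positive, for which the protocol sets no target. For cognition and other outcomes the direction of concern is the same, through enrichment, diagnostic mix and prior test exposure, but the documents give no figures from which to size it.

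**What to change.** In Goal 5:

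1. Add entry route (new versus rollover) and its interaction with time to age and sex.
2. For PET outcomes, also include tracer or use a harmonised scale, and say that this applies to the ADNI4-only dataset as well as the merged one.
3. Report the contrast in newly enrolled participants alone beside the pooled one. State how biomarker-based selection into the clinic cohort is handled, since the entry-route term does not correct selection that differs by race within new participants.
4. Show results adjusted for baseline diagnosis only as an alternative. Diagnosis may lie on the pathway from ethnocultural factors to the outcome, and adjusting for it could remove part of the difference under study.

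The cost is analysis wording, plus confidence intervals about 5 to 17% wider from the entry-route term. The interaction and tracer terms are not costed here; the new-only estimate rests on at most 750 participants.

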4.1.1 SAMPLE SIZE

Up to 1,500 participants will be enrolled to the in-clinic cohort of ADNI4 at approximately 65 sites in the United States and Canada. Up to 750 will be rollover participants from ADNI3, and up to 750 will be newly enrolled. Clinical/cognitive, imaging, biomarker, and genetic characteristics will be assessed across the three cohorts: CN, MCI, and DEM.

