7.4.1.1.3 Plasma and Serum Collection for Biomarkers

Plasma, serum, and buffy coat will be collected at Baseline from newly enrolled participants, and at the initial ADNI4 visit from rollover participants, and then ongoing during follow-up at In-Clinic Visits for all participants. All samples will be collected in the morning before breakfast and after an overnight fast (minimum 6 hour fast). Plasma and serum must be prepared at the site, frozen and then sent overnight on dry ice to the Biomarker Core at the UPENN. As above, buffy coat and red blood cells will be extracted from blood at the site and shipped overnight under ambient conditions to NCRAD.

LUMBAR PUNCTURE 7.4.2

The Lumbar Puncture procedure is optional for all participants. Should a newly enrolled or rollover participant agree to the optional LP, they will have CSF samples collected at Baseline and again every 2 years through the course of the ADNI4 study. All samples will be collected in the morning before breakfast and after an overnight fast (minimum 6 hours fast).

Approximately, 2 ml of CSF should be sent to the clinical laboratory of the Site PI for routine cell count, protein and glucose analyses. The majority of the CSF, at least 20 ml should be immediately frozen and sent overnight frozen on dry ice directly to the ADNI Biomarker Core laboratory for processing and storage in the ADNI Fluid Bank at UPENN.

Each study participant or a person designated to speak on their behalf will be contacted by phone 24 hours after the lumbar puncture to confirm the participant's well-being and to query about any new adverse events.

At the discretion of the Site PI (or Site Clinician), a coagulation panel (PT/PTT) may be obtained to rule out a clotting disorder. Also, per PI (or Site Clinician) discretion, anti-platelet agents (e.g., aspirin) may be discontinued for a period of time before and after the LP.

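### Goal 6 defines biomarker performance as a correlation or required sample size, but Friedman's rank test on participant contributions does not test equality of either

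*Protocol*

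**What the plan says.** Protocol section 8.2, Goal 6, sets out a formal comparison across biomarkers for all the preceding goals. It fixes three things.

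- The measure: "Biomarker performance will be operationalized as a correlation (for predictor) or required sample size for a clinical trial (screening tool/outcome").
- The unit of analysis: "Our comparison strategy first identifies dimension-free participant-level contributions to the correlation or to the formula for sample size".
- The test: "We compare biomarkers with Friedman's rank test to account for patient-level blocking, followed by pairwise comparisons adjusted for multiple comparisons".

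The protocol does not give the contribution formula, an alpha, a list of biomarkers to be compared, or their distributions. Goal 6 states no transformation.

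**The concern.** The measure and the test are both stated, and they do not match. A correlation is the mean of the participants' products of standardised marker and standardised outcome. A required sample size depends on a mean change and its variance. Friedman's test replaces the contributions by their within-participant ranks, so their size, which defines the measure, is lost. Its null hypothesis is that the biomarkers' contributions are exchangeable within a participant. Two biomarkers with the same correlation but different distribution shapes can violate that null.

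Shape differences are foreseeable, because the study compares amyloid and tau PET, MRI, CSF and plasma measures. At stake is which biomarkers Goal 6 reports as better, for prediction or for trial design.

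**Working it through.** **No figure to reproduce.** The protocol reports no number for Goal 6, so the check is a derivation followed by simulation.

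**Inputs from the protocol.** The measure, the unit and the test come from section 8.2, Goal 6. The largest number of blocks comes from section 4.1.1: "Up to 1,500 participants will be enrolled to the in-clinic cohort of ADNI4". Section 4.1.1.2 targets an 80% amyloid-positive rate among new participants, which motivates an 80:20 mixture as one assumed shape.

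**Assumptions.** Two-sided alpha is 0.05, two biomarkers are compared, and all marginal shapes are assumed. The contribution is z_x·z_y for the correlation and change/SD for sample size.

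**Step 1: what each quantity measures.**

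- Correlation: r = (1/n) Σ z_x,i z_y,i, a mean of contributions.
- Required sample size: proportional to (σ/μ)², where μ and σ are the mean and SD of change. Equal μ/σ means equal required sample size.
- Friedman with two biomarkers: Q = (2w − n)²/n, where w counts participants whose contribution from A exceeds that from B. This is a sign test of P(A > B) = 0.5, and neither r nor μ/σ enters it.

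**Step 2: why a larger n makes it worse.** Q exceeds 3.84 when w/n differs from 0.5 by more than 0.98/√n:

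- n=300: 0.98/17.3 = 5.7 percentage points
- n=600: 0.98/24.5 = 4.0 points
- n=1,500: 0.98/38.7 = 2.5 points

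A shape difference that moves P(A > B) by a few points, with r unchanged, becomes significant as n rises.

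**Step 3: equal correlations.** The model is Y = b(A + B) + e, with A and B independent and standardised, so both correlations equal b = 0.40. The mixture has component means 0 and 2 and SD 0.5. Each cell uses about 1,000 datasets; ranges show separate runs.

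| Marker shapes | n=300 | n=600 | n=1,500 |
|---|---|---|---|
| Normal vs normal | 4% | 4% | 4-5% |
| 80:20 mixture vs normal | 5% | 4% | 6% |
| Normal vs lognormal, log-SD 0.4 | 6-8% | 7% | 16-18% |
| 80:20 mixture vs lognormal 0.8 | 25% | 42% | 82% |
| Normal vs lognormal 0.8 | 31-35% | 54-57% | 93-94% |
| 50:50 mixture vs lognormal 0.8 | 77-80% | 96-97% | 100% |

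Entries are Friedman's false-rejection rates. A paired large-sample test of the difference in correlations, tried alongside, rejected in 4-8% of datasets. Under a different joint model for markers and outcome, normal vs lognormal 0.8 gave 27-34% at n=1,500. The size therefore depends heavily on the assumptions, but the direction does not.

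**Step 4: unequal correlations, 0.40 vs 0.50.** Friedman significantly favoured the weaker marker as follows:

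- 50:50 mixture (0.40) vs lognormal 0.8 (0.50): 69-71% at n=300 and 100% at n=1,500
- 80:20 mixture vs lognormal 0.8: 10-12% and 39-43%
- 80:20 mixture vs lognormal 0.4: at most 1%
- 50:50 mixture vs normal: 3% and 5%

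In the first case the paired test favoured the weaker marker in at most 0.3% of datasets.

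**Step 5: power where the level is right.** With normal markers, r 0.4 vs 0.3 and n=1,500, Friedman had about 42% power and the paired test 86%. A second generating model gave 47% and 89%.

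**Step 6: the sample-size measure.** With standardised change 0.5 for both markers (equal required sample size), n=1,500, normal vs skewed change:

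- Friedman rejected in 37-84% of datasets when the changes were independent, and in 34-67% when they were correlated 0.3 to 0.8. The paired test of μ/σ rejected in 4-9%.
- With 0.45 vs 0.50, the weaker marker needs (0.50/0.45)² = 1.23 times the sample size. Friedman favoured it in 8-42% of datasets (independent) or 1-17% (correlated).

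**The case against.** **Rates.** The strongest reply is that no error rate can be attributed to the plan. The documents give no distribution, alpha or contribution formula, and the results move several-fold with assumptions. This stands. A reader might infer that the test nearly always declares equal biomarkers different or picks the weaker one. The documents do not support that: same-shape markers keep about the nominal level, mild skew inflates it modestly, and reversal is rare in many moderate settings.

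**Safeguards.** Goal 4 allows continuous measures to be "possibly transformed to deal with floor or ceiling effects, nonlinearity, practice effects, nonnormality, or heteroscedasticity", and section 8.1 adds: "Secondary analyses will assess the potential impact of missing data, outliers, and other questions regarding sensitivity and robustness of findings". Either could soften or reveal the problem. The first is optional and stated for the Goal 4 mixed models; the second is general. Neither changes the hypothesis that Goal 6 tests.

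**Detail left to a SAP.** The contribution formula, transformations and handling of missing blocks can properly be left there. The pairing of measure and test cannot be excused this way, because the protocol states both.

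**Complete blocks and tracers.** "The Lumbar Puncture procedure is optional for all participants" (section 7.4.2), so a reader might infer that any comparison including CSF shrinks every block to those who consent to it. Section 7.3.1.2 says "Each participant will be assigned to one amyloid tracer and one tau tracer", so a reader might infer a failed within-participant comparison of tracers. Goal 6 states neither plan: it does not require one complete-case set, and it does not say that tracers will be compared as blocks. Comparing tracers as independent groups would not be a safe remedy either, since new participants' tracers follow site proximity and rollovers keep their ADNI3 tracers, which confounds tracer with site and cohort.

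**Importance.** A reader might call this the study's headline comparison. It is one of six goals in a non-randomised natural history study, and the correlations and sample sizes can be reported directly.

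**Conclusion.** The concern holds: the stated test does not address the stated measure, whatever contribution formula is chosen. The size is conditional. Under the illustrative models at n=1,500 with both correlations 0.40, false rejection runs from about 4-5% (same shape) through 16-18% (normal vs lognormal 0.4) and 82-93% (80:20 mixture or normal vs lognormal 0.8) to 100% (50:50 bimodal vs lognormal 0.8). For some shape pairs the weaker marker is favoured. With normal markers the level is sound, but power is roughly halved in the case examined. These results rest on assumed shapes, an assumed alpha of 0.05 and assumed contributions. They show what the method can do and do not forecast ADNI4's results. Severity: should fix.

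**What to change.** In Goal 6, replace Friedman's test with a paired comparison of the measure itself:

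- Resample participants, and recompute each biomarker's correlation or log required sample size in every resample.
- Report a bootstrap confidence interval for each pairwise difference, with Holm adjustment across pairs.
- For each pair, use the participants who have both measures.
- For the correlation measure, a test for dependent correlations is an acceptable alternative.

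Resampling whole participants keeps the within-person pairing that Friedman's test was chosen to respect. The cost is analysis wording and computing time; no data collection or visit changes.

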7.3.1.4 DATA MANAGEMENT AND QUALITY CONTROL

Images are uploaded by site users to the Laboratory of Neuroimaging (LONI) at the University of Southern California. Data are deidentified as part of the upload and placed into quarantine until they pass quality assurance evaluation conducted by the PET Core. The aim of this work is not only to make sure that all PET scans are acquired and reconstructed using the appropriate protocols and

that image quality is good, but also to standardize the images from the different sites (and hence the different PET scanner vendors and models) as much as possible in order to reduce inter-site differences.

Quality control of scans could necessitate salvage with reprocessing of the raw imaging data. All sites are required to save original PET data for the duration of the study.

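### Goal 6 takes participants as independent blocks although they are nested in about 65 sites, so the level of the biomarker comparison is not assured if their contributions share site-by-biomarker effects

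*Protocol*

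**What the plan says.** Goal 6 covers the formal comparison of biomarkers for all the earlier goals. The ranked quantity is not the biomarker value: "Our comparison strategy first identifies dimension-free participant-level contributions to the correlation or to the formula for sample size". The test follows: "We compare biomarkers with Friedman's rank test to account for patient-level blocking". Multiplicity-adjusted pairwise tests come after it. The participant is the only source of dependence named, and Section 8 does not mention site, scanner or clustering.

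Other parts of the protocol describe a second level:

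- Section 4.1.1: "Up to 1,500 participants will be enrolled to the in-clinic cohort of ADNI4 at approximately 65 sites", and "Up to 750 will be rollover participants from ADNI3, and up to 750 will be newly enrolled".
- Section 7.3.1.2, on tracers: "Participants that are newly recruited to ADNI4 will be assigned to tracers based on the clinical site proximity to PET tracer manufacturing sites". Rollover participants keep the ligand they had in ADNI3.
- Sections 7.3.1.1 and 7.3.2.1: PET and MRI scanners are qualified site by site.
- Section 7.3.1.4: PET images from different sites are standardized "as much as possible in order to reduce inter-site differences", that is, differences are reduced and not claimed to vanish.
- Section 8.1: harmonization across protocols, assays and tracers is described for the merged data from all ADNI phases.

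**The concern.** Blocking on the participant removes whatever is common to all biomarkers in one person. It does not remove an effect that raises or lowers one biomarker's contribution relative to the others for many people at the same site. A scanner or tracer that makes one measure perform better or worse locally would be such an effect. The within-participant rankings would then be correlated within site. Friedman's null distribution would be too narrow, and every unadjusted pairwise p-value would be too small. The multiplicity adjustment starts from those p-values and cannot repair them.

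Goal 6 is the step at which one biomarker is declared better than another, and it bears on the choice of trial outcome measures under Aim 2. A site pattern read as a biomarker difference would carry into that advice.

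**Working it through.** **Inputs from the protocol.** N up to 1,500 (750 + 750) and about 65 sites. That is 1,500/65 = 23.1 participants per site, or 750/65 = 11.5 new participants per site. There is no error rate or sample-size figure for Goal 6 to reproduce.

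**Assumptions.** The level, the number of biomarkers k, the ICC and the contribution formula are not given. I take a level of 0.05, k = 3 and 5, 65 equal sites, and ICC 0.01 to 0.10 for the site-by-biomarker component. All biomarkers perform equally on average, so every rejection is false.

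**Step 1: rough size for one pairwise contrast.** Design effect = 1 + (m − 1) × ICC; the two-sided error is that of a normal statistic with critical value 1.96/√(design effect).

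- N = 1,500, ICC 0.05: 1 + 22.1 × 0.05 = 2.10; 1.96/√2.10 = 1.35; error 17.7%.
- N = 750, ICC 0.05: 1 + 10.5 × 0.05 = 1.53; 1.96/√1.53 = 1.59; error 11.3%.

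**Step 2: site effect placed directly in the contributions.** Simulated rejection rates, N = 1,500:

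| ICC | Friedman, k = 3 | Friedman, k = 5 |
|---|---|---|
| 0 | 0.047 | 0.053 |
| 0.01 | 0.073 | 0.092 |
| 0.05 | 0.191 | 0.277 |
| 0.10 | 0.324 | 0.496 |

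A site-clustered Wald test on the same ranks gave 0.045 to 0.056 throughout. A site shift common to all biomarkers gave 0.055 and 0.044 with Friedman's test: it cancels. This step shows the mechanism only, because it assumes that the contributions cluster. Steps 3 and 4 build them.

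**Step 3: correlation metric.** Contribution = z(biomarker) × z(outcome), N = 1,500.

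- Site offset in the biomarker only, ICC 0.05 to 0.20: 0.019 to 0.048.
- Site scale differences, SD 20%: 0.026 to 0.043.
- Biomarker ICC 0.20 with outcome ICC 0.10: 0.060 to 0.087.
- Correlation varying by site around 0.4 with SD 0.1: 0.054 (k = 3) and 0.048 (k = 5), against 0.037 and 0.026 with no site effect.
- The same with SD 0.2: 0.118 (k = 3), and 0.158 and 0.179 in two separate runs (k = 5). Clustering on site gave 0.042 and 0.038.

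An SD of 0.2 around 0.4 is wide: two SDs either side runs from 0 to 0.8. A squared-difference form of the contribution gave 0.195 at that SD (k = 3), against 0.056 clustered.

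**Step 4: sample-size metric.** Contribution = change divided by its SD, N = 1,500.

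| Site effect | Friedman, k = 3 | Friedman, k = 5 |
|---|---|---|
| None | 0.059 | 0.071 |
| All biomarkers and participants, ICC 0.01 | 0.093 | 0.114 |
| All biomarkers and participants, ICC 0.05 | 0.202 | 0.311 |
| Two PET markers, new participants only | 0.077 | 0.101 |

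With site as cluster the rates were 0.054 to 0.065. With no site effect the two tests agreed, so the small excess in the first row does not come from clustering. A form built on squared deviations with site scale differences reached at most 0.074.

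**The case against.** A reader might infer that site-based tracer assignment makes Goal 6 declare false differences far more often than 5%. The documents do not support that.

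- No ICC, level, number of biomarkers or formula is stated. Inflation is absent at ICC 0 and small at ICC 0.01.
- The test ranks contributions, not biomarker values. For the correlation metric, offsets and scale shifts in the biomarker alone produced no inflation.
- Tracers follow site for at most 750 of 1,500 participants. Restricting the site effect to PET markers in that group brings the error close to its no-site-effect value.
- PET scans are standardized centrally, MRI qualification requires exact execution of the protocol, and Section 9.1.1.6 describes highly standardized CSF and plasma assays. An equally strong site effect on every biomarker is therefore an upper case.

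All of this stands, and it is why the size is stated conditionally.

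The remaining objection is that Section 8 is a short summary and that site handling belongs in the statistical analysis plan. This has weight: that plan is not shown and may add it. But the protocol is not merely silent here. It names the test and the block, so a plan that implements Goal 6 as written inherits the independence assumption. Standardization and harmonization make site effects smaller; they do not make the test valid where some remain.

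**Conclusion.** The point holds in conditional form. As specified, Goal 6 has no protection against contributions that share a site-by-biomarker component, and its nominal level is then not assured. How far the error exceeds 5% cannot be derived from the protocol. Under the stated assumptions it ranges from little or none (most correlation cases, and PET-only effects in new participants) to about 20 to 31% (standardized change, ICC 0.05 in all biomarkers and participants). Equal site sizes were assumed; unequal sizes raise the error where contributions do cluster. Site effects common to all biomarkers do no harm. This is a worthwhile and cheap correction, not evidence that the planned comparison will mislead.

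**What to change.** In Goal 6, keep the participant-level contributions and their within-participant pairing, but take site as the independent unit. P-values and confidence intervals for the overall and the pairwise comparisons would come from either a bootstrap that resamples whole sites, or a site-cluster-robust test on the contributions or their ranks. The multiplicity adjustment is then applied to those p-values. The contribution formula should be written out in the same place, since the size of the problem depends on it.

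The cost is a sentence or two in Section 8.2, the matching text in the statistical analysis plan, and a change of resampling unit in the code. No new data are needed, because participants are enrolled and followed by site. The downside is wider intervals and fewer declared differences where site effects exist. Where they do not, results hardly change.
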